2.2 Study Endpoints

2.2.1 Primary Endpoint

- The ACR CRISS composite score (0-1) at Week 52

2.2.2 Secondary Efficacy Endpoints

- Change in HAQ-DI from baseline at Weeks 16, 26, 39, and 52.
- Change in Patient Global Assessment from baseline at Weeks 16, 26, 39, and 52.
- Change in percent predicted forced vital capacity (%pFVC) from baseline at Weeks 16, 26, 39, and 52.
- Change in Physician Global Assessment from baseline at Weeks 16, 26, 39, and 52.
- Change in mRSS from baseline at Weeks 16, 26, 39, and 52.
- ACR CRISS Score at Weeks 16, 26, and 39.
- ACR CRISS Score improvement at Weeks 16, 26, 39 and 52: Proportion of subjects with $\geq 25\%$ improvement in mRSS, HAQ-DI, Patient Global Assessment, Physician Global Assessment, or $\geq 5\%$ improvement in FVC for at least 3 of the 5 ACR CRISS measures.
- ACR CRISS score responder (CRISS ≥ 0.6) at Weeks 16, 26, 39, and 52..

2.2.3 Exploratory Efficacy Endpoints

2.2.4 Safety Endpoints

- Treatment-emergent adverse events ([TEAEs] including serious adverse events [SAEs], AEs leading to withdrawal, and adverse events of special interest [AESIs]).
- Physical examination.
- Vital signs (blood pressure, pulse rate, respiratory rate, and body temperature).
- Clinical laboratory examinations (hematology, coagulation, biochemistry, and urinalysis), including liver function markers (ALT, AST, gamma glutamyl transpeptidase [GGT], ALP, direct and total bilirubin).
- 12-lead electrocardiogram (ECG).
- Nevi (Melanocytic Lesions) appearance (assessed by a dermatologist or other qualified site staff). Any nevi (Melanocytic Lesions) undergoing change of clinical concern during active treatment will be biopsied for follow-up and evaluated by a central pathology laboratory.

2.2.5 Pharmacokinetics Endpoint

- Assessment of plasma concentrations of MT-7117 measured at scheduled visits.

3 STUDY DESIGN

3.1 Study Design

This is a Phase 2, multicenter, randomized, double-blind, placebo-controlled, parallel-group study to evaluate efficacy, safety, and tolerability of MT-7117 in subjects with dcSSc.

The duration of the study is approximately 60 weeks; screening period up to 4 weeks, double-blind treatment period of 52 weeks, and a safety follow-up period of 4 weeks after last dose.

Following completion of the all screening assessments, subjects will return to the clinical site for start of the double-blind treatment period (Visit 2, Day 1) and baseline assessments will be evaluated and confirmed the eligibility (e.g., safety assessments, ACR CRISS components, and nevi (Melanocytic Lesions) evaluation, if nevi (Melanocytic Lesions) are present.

Eligible subjects will be randomized in a 1:1 ratio to either MT-7117 at starting of [REDACTED] every day (QD) or matching placebo in a double-blind manner, stratified by autoantibody status of [REDACTED] performed at screening (positive or negative).

Study drug will be administered once daily orally in the morning with or without food.

During the double-blind treatment period, subjects will return to the clinical site and assessments will be collected as described in protocol.

The decision about dose reduction and tolerability should be made according to the pre-specified criteria and the Investigator's clinical judgment.

If a subject is experiencing intolerance to study drug, they should first be conservatively managed using standard of care and maintain the starting dose of study drug (active or placebo).

If the subject continues to present significant intolerable AEs at the following scheduled or unscheduled visit and the Investigator deems it necessary, the daily dose of study drug can be reduced from [REDACTED] QD to [REDACTED] QD while tolerability is managed with standard of care.

If the subject continues to present significant intolerable AEs at the following scheduled or unscheduled visit and the Investigator deems it necessary, the dose of study drug can be reduced from [REDACTED] QD to [REDACTED] QD.

If the subject continues to present significant intolerable AEs at the decreased dose of [REDACTED] QD and the Investigator deems it necessary, the subject may discontinue study treatment.

All dose reductions during the Treatment Period will be done in [REDACTED] decrements. Dose reductions will be conducted via the Interactive Web-based Response System (IWRS).

Subjects who do not tolerate a minimum dose of [REDACTED] day will be withdrawn from the study.

Subjects with worsening scleroderma such as skin thickening or other scenarios will be allowed to use rescue therapy starting at or after Week 26, and those with confirmation

of predicted FVC decline (after 2 separate confirmations within 4 weeks via an unscheduled visit) will be allowed to use rescue therapy starting at or after Week 16.

End of treatment (EOT) or early termination (ET) assessments will be performed for all subjects, who will undergo efficacy and safety evaluations. Efficacy evaluations will include change in the composite score of ACR CRISS Components, PGIC, PGIS, UCLA SCTC GIT 2.0 questionnaire, PROMIS-29 test questionnaire, and certain biomarkers.

[figure not shown]
Subjects who discontinue study treatment before EOT (Week 52) should be encouraged to continue in the study and complete all the required study assessments through Week 52.

If a subject decides to permanently withdraw consent from the study, every attempt should be made to have the subject complete the ET visit and complete the study assessments listed at Week 52.

In the event a subject does not return to the clinical site for the ET and/or safety follow-up visit, the Investigator must make every effort to contact the subject by telephone to for the collection and source documentation of safety information such as AEs, dosing compliance, and review of concomitant medications and date of last dose of study drug. Return of unused medication will be performed by courier where allowed.

A safety follow-up visit will occur at Week 56 (Visit 9) for subjects who complete the double-blind treatment period (Week 52) and 4 weeks after the last dose of study drug for subjects who ET from the study.

Further details can be found in the Study Schema below.

- a) Starting daily dose will be MT-7117 [REDACTED] QD or matching placebo, with possibility to reduce the dose in a stepwise manner from [REDACTED] QD to [REDACTED] QD and possibly from [REDACTED] QD to [REDACTED] QD to manage subjects' tolerability to study drug.
- b) At the discretion of the Investigator, rescue therapy may start as early as Week 16 with confirmation of predicted FVC decline, and as early as Week 26 with worsening scleroderma such as skin thickening or other scenarios.

Figure 1 Study Design Schema

3.2 Schedule of Study Procedures

Study assessments and corresponding event schedules are summarized in the time and events schedule. The schedule of assessment is shown in [REDACTED]

Table 1: Schedule of Activities

	Screening period	Double-blind Treatment Period						Safety Follow-up Period
		1	2	3	4	5	6	
Visit Number							6A Telephone Visit	
Study Week	-4	1	2	3	4	5	6	7 Telephone Visit
Study Day ± Window	-28 to -1	(Baseline)	15 (± 3 days)	43 (± 5 days)	113 (± 7 days)	183 (± 7 days)	274 (± 7 days)	393 (± 7 days)
Informed consent	X							
Inclusion/exclusion criteria	X	X						
Prior medications	X							
Demographics	X							
Medical history	X							
Randomization	X							
Dispensing of study drug	X	X	X	X	X	X	X	
Drug accountability	X	X	X	X	X	X	X	
Body weight	X	X	X	X	X	X	X	
Height	X							

Statistical Analysis Plan
Protocol No. MT-7117-G02

Mitsubishi Tanabe Pharma Development America

	Screening period	Double-blind Treatment Period						Safety Follow-up Period		
		1	2	3	4	5	6	7	8	9 ^a (EOS)
Visit Number										
Study Week	-4	1	2	6	16	26	32	39	45	52
Study Day ± Window	-28 to -1	(Baseline) (± 3 days)	15	43	113	183	225	274	316	365
			(± 5 days)	(± 7 days)	(± 7 days)	(± 7 days)				
Physical examination ^b	X	X	X	X	X	X	X	X	X	X
Vital signs ^c	X	X	X	X	X	X	X	X	X	X
12-lead ECG	X				X					X
SSc-specific autoantibody test ^d	X									
■■■■■	X									
■■■■■	X					X				
■■■■■							X			
■■■■■								X		
Pregnancy test ^e	X	X	X	X	X	X	X	X	X	X

Confidential

	Screening Period	Double-blind Treatment Period										Safety Follow-up Period
		1	2	3	4	5	6	7	8	9 ^a	9 ^a	
Visit Number	6A Telephone Visit	7	Telephone Visit	8 (EOT/ET)	9 ^a (EOS)							
Study Week	-4	1	2	6	16	26	32	39	45	52	56	
Study Day ± Window	-28 to -1 (Baseline)	15 (± 3 days)	43 (± 5 days)	113 (± 7 days)	183 (± 7 days)	225 (± 7 days)	274 (± 7 days)	316 (± 7 days)	365 (± 7 days)	393 (± 7 days)	393 (± 7 days)	
Hematology/coagulation, biochemistry, and urinalysis ^f	X	X	X	X	X	X	X	X	X	X	X	
ESR ^e	X											
PK sampling (blood) ^h	X	X	X	X	X	X	X	X	X	X	X	
Blood sampling for		X					X					
	[REDACTED]	[REDACTED]	[REDACTED]	[REDACTED]	[REDACTED]	[REDACTED]	[REDACTED]	[REDACTED]	[REDACTED]	[REDACTED]	[REDACTED]	
	[REDACTED]	[REDACTED]	[REDACTED]	[REDACTED]	[REDACTED]	[REDACTED]	[REDACTED]	[REDACTED]	[REDACTED]	[REDACTED]	[REDACTED]	
	[REDACTED]	[REDACTED]	[REDACTED]	[REDACTED]	[REDACTED]	[REDACTED]	[REDACTED]	[REDACTED]	[REDACTED]	[REDACTED]	[REDACTED]	
	[REDACTED]	[REDACTED]	[REDACTED]	[REDACTED]	[REDACTED]	[REDACTED]	[REDACTED]	[REDACTED]	[REDACTED]	[REDACTED]	[REDACTED]	
	[REDACTED]	[REDACTED]	[REDACTED]	[REDACTED]	[REDACTED]	[REDACTED]	[REDACTED]	[REDACTED]	[REDACTED]	[REDACTED]	[REDACTED]	
	[REDACTED]	[REDACTED]	[REDACTED]	[REDACTED]	[REDACTED]	[REDACTED]	[REDACTED]	[REDACTED]	[REDACTED]	[REDACTED]	[REDACTED]	

Statistical Analysis Plan
Protocol N8-MT-7117-G02

Mitsubishi Tanabe Pharma Development America

Confidential

Statistical Analysis Plan
Protocol No. MT-7117-G02

Statistical Analysis Plan
Protocol No. MT-7117-G02

Mitsubishi Tanabe Pharma Development America

Confidential

Page 18 of 72

Statistical Analysis Plan
Protocol No. MT-7117-G02

Abbreviations: ACR CRISS = American College of Rheumatology Composite Response Index for Systemic Sclerosis; ECG = electrocardiogram; EOS = End of Study; EOT = End of treatment; [REDACTED]

SHAQ= Scleroderma Health Assessment Questionnaire ; HIV = human immunodeficiency virus; mRSS = modified Rodnan Skin Score; [REDACTED]

%pFVC = percent predicted forced vital capacity; [REDACTED]

[REDACTED]; PK = pharmacokinetic; [REDACTED]

[REDACTED]; MC1R= melanocortin-1 receptor; SNPs= single-nucleotide polymorphisms, PhGA=Physician Global Assessment; PtGA=Patient Global Assessment; ET=Early Termination; AE=Adverse Event; eCRF=

electronic Case Report Form; HAQ-DI= Health Assessment Questionnaire Disability Index; VAS= Visual Analog Scale

a. All subjects (completers and those who ET) will return to the clinical site 4 weeks after their last dose for a safety follow-up visit. For subjects who ET and will not revisit the clinical site, the site will perform a scheduled phone call for the collection of safety assessments (e.g., AEs, concomitant medication, and date of last dose of study drug).

b. A complete physical examination will be performed at Visit 1 and an abbreviated physical examination will be performed at all other specified time points.

c. Vital signs will include blood pressure, pulse rate, respiratory rate, and body temperature (e.g., oral, axillary or tympanic body temperature).

d. [REDACTED].

e. For female subjects of child-bearing potential, a serum pregnancy test will be performed at Visit 1, a urine pregnancy test (on-site) will be performed at all other site visits,

and a urine dipstick pregnancy test at home or other home testing arrangements will be performed at Telephone Visits (Visit 6A and 7A).

f. Refer to [REDACTED] for laboratory evaluations.

g. ESR will be analyzed locally at the site level and at Screening only.

h. PK blood samples for MT-7117 will be collected at Visit 2 predose, Visits 3, 4, 5, 6, 7, and Visit 8 at any time during each visit. Date and time of study drug dose and date

and time of PK sample collection will be recorded.

i. Blood sampling will be collected for optional PGx analysis for those subjects who have provided informed consent.

j. [REDACTED]

1. [REDACTED] s.
- m. SHAQ is composed of HAQ-DI and VAS.
- n. [REDACTED]
- o. Nevi (Melanocytic Lesions) evaluation will be performed by a local dermatologist or qualified site staff. Baseline nevi (Melanocytic Lesions) evaluation will be performed at any time during the screening period before randomization at Visit 2 (Day 1). The nevi (Melanocytic Lesions) evaluation at Visit 9 is to assess for the reversibility if any suspicious nevi (Melanocytic Lesions) changes that were observed during treatment as per the Investigator's (and/or dermatologist's or other qualified site staff) judgment. Any follow-up will be recorded in the eCRF. Nevi (Melanocytic Lesions) assessment will be described in a separate document.
- p. Subjects will be asked whether they believe they received active or placebo treatment.
- q. Concomitant medications at screening, baseline and used during study treatment will be reviewed, recorded and discussed with the Sponsor and medical Monitor (as needed).
[REDACTED]

3.2.1 Screening Phase and Rescreening

Screening assessments will be performed up to 28 days prior to Day 1 of the double-blind treatment period. All screening evaluations must be completed and reviewed to confirm that potential subjects meet all eligibility criteria.

At the end of the screening period, if a subject has not met all eligibility criteria at the end of the screening period, the subject will be registered as a screen failure. Screen failures may be eligible for rescreening 1-time following consultation with the Sponsor and Medical Monitor.

Note: If the rescreening occurs more than 30 days after the first screening and signing of the original ICF, all screening procedures, including ICF, must be repeated. If within 30 days, repeat assessments should be discussed with the Medical Monitor.

If a subject does not meet eligibility criteria for laboratory and pulmonary function tests (PFTs), the subject may undergo repeat laboratory and PFTs up to 2 additional times during the 4-week screening period. Repeat of laboratory or PFTs is not considered rescreening.

3.2.2 Double-blind Treatment Period

Subjects who successfully complete the screening period will return to the clinical site on Day 1 of the double-blind treatment period to reconfirm his/her eligibility by reviewing the inclusion and exclusion criteria and evaluate other baseline criteria prior to randomization. To be randomized into the double-blind treatment period, the subject must meet the required criteria at screening and at baseline. Eligible subjects will be randomized, and study drug administration will begin on Day 1 (Visit 2) after confirmation of all baseline criteria.

Study visits will occur at the study site per the Schedule of Assessments (Table 1).

3.2.3 Dose Reduction Visit

If a subject experience any intolerable AEs, the dose can be reduced. Subjects with intolerable AEs, will have to come back to the clinical site for an unscheduled visit where the following procedures will be performed:

- Physical examination including vital signs.
- Adverse events and concomitant medications, if any, will be assessed since from the previous visit.
- Local urine pregnancy test (if applicable).
- Safety blood and urine samples will be collected and submitted to the central laboratory for analysis.

- Study drug will be collected, IWRS will allocate new study drug, and treatment compliance will be reviewed.

If a dose reduction is deemed necessary by the Principal Investigator, the IWRS will be used for assignment of the new [REDACTED] packs to be provided to the subject for dose reduction and study drug dispensation. The date of dose reduction visit and the reason will be recorded in the eCRF.

3.2.4 Dose Reduction Criteria

Subjects will be informed regarding potential side effects. If the side effects experienced by subjects are not manageable through nonpharmacologic and pharmacologic treatment (using standard of care), dose reduction (from [REDACTED] QD to [REDACTED] QD, or from [REDACTED] QD to [REDACTED] QD) should be considered to manage the incidence and/or intensity of the subject-reported AEs (including but not limited to vomiting, diarrhea, headache, hyperpigmentation).

For safety reasons, the Investigator may also decide to implement a dose reduction for a subject. The following are criteria for Investigator initiated dose reduction:

- AEs which are classified as serious and/or moderate/severe (in severity), which did not improve with clinical management according to standard of care per Investigator's judgement, AND
- AEs assessed as having reasonable possibility of relationship to MT-7117 per Investigator's judgement.

Examples of severe AEs include AE which limit self-care activities of daily living (independently eat, dress, walk/transfer from 1 position to another, bathe, toilet, maintaining bowel/bladder continence).

Note: Dose interruption can be considered after the discussion with the Sponsor Medical Monitor in the case, such as

- 1) in subjects with suspicious lesions or change in nevi (Melanocytic Lesions) that had their dose temporarily interrupted can resume study treatment at the same dose they were interrupted at after the evaluations are complete and nevi (Melanocytic Lesions) and/or other lesions are determined to be benign; or
- 2) in a subject with an initial positive urine pregnancy test, awaiting a confirmatory test. If the confirmatory test is definitively negative, dosing may resume at the same dose they were interrupted; or

3) in a subject with any laboratory or clinical abnormality such as meeting the criteria of AESI, awaiting a confirmatory test and/or a judgement whether it is clinically significant. Resumption of dosing at the same dose they were interrupted will be considered based on the discussion with the Sponsor Medical Monitor and Investigator and should be closely followed up.

At any time during the study, subjects may be withdrawn from study treatment if continuing study treatment would be detrimental to the subject's safety in the opinion of the Investigator.

3.3 Sample Size and Power Considerations

The planned sample size of 72 is expected to provide power for the comparison between MT-7117 treatment group and placebo group for ACR CRISS score at Week 52. The calculation of sample size assumes a 2-sided alpha level of 0.05 and uses EAST (Version 6.5) for Wilcoxon Mann Whitney test. The randomized 72 subjects (36 subjects for MT-7117 and 36 subjects for placebo) with a 1:1 allocation ratio would provide 80% power to detect treatment difference of 0.35 (35% improvement on MT-7117 treatment group compared to placebo group) in ACR CRISS score at Week 52 with an associated standard deviation (SD) of 0.5.

4 PLANNED ANALYSIS

4.1 Interim analysis and Data Monitoring Committee

No formal interim analysis of efficacy/safety data will be conducted prior to collection of all data necessary for the statistical analysis.

An external independent Data Monitoring Committee (iDMC) will be established to perform regular review of the safety data to ensure the ongoing safety and risk-benefit of participating subjects until the last subject completes the double-blind treatment period. The frequency of data review will be described in the iDMC Charter. The safety monitoring analyses required for the iDMC's review will be performed by Cytel Inc. which is a Contract Research Organization. These interim analyses are described in the iDMC Statistical Analysis Plan (SAP).

4.2 Final Analysis

Final Analysis will take place after the study complete and data base is locked. The analyses defined in this document will be performed.

5 ANALYSIS POPULATIONS

5.1 Randomized (RAND) Population

The Randomized (RAND) population includes all randomized subjects.

5.2 Intent-to-Treatment (ITT) Population

The Intent to treat (ITT) population includes all randomized subjects who receive at least 1 dose of study drug. The ITT population will be used for all efficacy analyses. The subject randomized treatment will be used for efficacy analyses.

5.3 Per-protocol (PP) population

The per-protocol population includes all ITT subjects who do not have to be excluded due to relevant protocol deviations (to be discussed in the blinded data review meeting) and who complete Week 52 (the end of double blinded treatment period). The PP will be used to perform supportive analysis for the only primary endpoint (CRISS).

5.4 Safety (SAF) Population

The safety analysis population is defined as all randomized subjects who received at least 1 dose of study drug. The safety population will be used for all safety analyses. The subject actual treatment received will be used for safety analyses. For subjects who took more than one treatment, the highest dose level will be used for safety analyses.

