8 STUDY DESIGN

8.1 Overall Study Design

This is a Phase 2, multicenter, randomized, double-blind, placebo-controlled, parallel-group study to evaluate efficacy, safety, and tolerability of MT-7117 in subjects with dcSSc.

The duration of the study is approximately 60 weeks; screening period up to 4 weeks, double-blind treatment period of 52 weeks, and a safety follow-up period of 4 weeks after last dose.

Following completion of the all screening assessments, subjects will return to the clinical site for start of the double-blind treatment period (Visit 2, Day 1) and baseline assessments will be evaluated and confirmed the eligibility (e.g., safety assessments, ACR CRISS components, and nevi (Melanocytic Lesions) evaluation, if nevi (Melanocytic Lesions) are present (Table 1)

Eligible subjects will be randomized in a 1:1 ratio to either MT-7117 at starting of 300 mg every day (QD) or matching placebo in a double-blind manner, [REDACTED]

Study drug will be administered once daily orally in the morning with or without food.

During the double-blind treatment period, subjects will return to the clinical site and assessments will be collected as described in Table 1.

The decision about dose reduction and tolerability should be made according to the pre-specified criteria and the Investigator's clinical judgment.

If a subject is experiencing intolerance to study drug, they should first be conservatively managed using standard of care and maintain the starting dose of study drug (active or placebo).

If the subject continues to present significant intolerable AEs at the following scheduled or unscheduled visit and the Investigator deems it necessary, the daily dose of study drug can be reduced from 300 mg QD to 200 mg QD while tolerability is managed with standard of care.

If the subject continues to present significant intolerable AEs at the following scheduled or unscheduled visit and the Investigator deems it necessary, the dose of study drug can be reduced from 200 mg QD to 100 mg QD.

If the subject continues to present significant intolerable AEs at the decreased dose of 100 mg QD and the Investigator deems it necessary, the subject may discontinue study treatment.

All dose reductions during the Treatment Period will be done in 100 mg decrements. Dose reductions will be conducted via the Interactive Web-based Response System (IWRS).

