10.1.3.1 Dose Reduction Visit

If a subject experience any intolerable AEs, the dose can be reduced as described below in Section 10.1.3.2. Subjects with intolerable AEs, will have to come back to the clinical site for an unscheduled visit where the following procedures will be performed:

- Physical examination including vital signs.
- Adverse events and concomitant medications, if any, will be assessed since from the previous visit.
- Local urine pregnancy test (if applicable).
- Safety blood and urine samples will be collected and submitted to the central laboratory for analysis.

- Study drug will be collected, IWRS will allocate new study drug, and treatment compliance will be reviewed.

If a dose reduction is deemed necessary by the Principal Investigator, the IWRS will be used for assignment of the new blister packs to be provided to the subject for dose reduction and study drug dispensation. The date of dose reduction visit and the reason will be recorded in the eCRF.

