10.1.3.2 Dose Reduction Criteria

Subjects will be informed regarding potential side effects. If the side effects experienced by subjects are not manageable through nonpharmacologic and pharmacologic treatment (using standard of care), dose reduction (from 300 mg QD to 200 mg QD, or from 200 mg QD to 100 mg QD) should be considered to manage the incidence and/or intensity of the subject-reported AEs (including but not limited to vomiting, diarrhea, headache, hyperpigmentation).

For safety reasons, the Investigator may also decide to implement a dose reduction for a subject. The following are criteria for Investigator initiated dose reduction:

- AEs which are classified as serious and/or moderate/severe (in severity), which did not improve with clinical management according to standard of care per Investigator's judgement, AND
- AEs assessed as having reasonable possibility of relationship to MT-7117 per Investigator's judgement (Section 14.5).

Examples of severe AEs include AE which limit self-care activities of daily living (independently eat, dress, walk/transfer from 1 position to another, bathe, toilet, maintaining bowel/bladder continence).

Note: Dose up-titration after dose reduction is not allowed.

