8.3.1 Adverse Events

The overall TEAEs are summarized by Placebo, MT-7117 over all, MT-7117 [REDACTED] only, [REDACTED] to [REDACTED] regimen, [REDACTED] to [REDACTED] regimen for subjects with

- at least one TEAE,
- at least one treatment emergent adverse reaction,
- at least one serious TEAE,
- at least one serious treatment emergent adverse reaction,
- at least one TEAE leading to drug withdrawn,
- at least one treatment emergent adverse reaction leading to drug withdrawn,
- at least one hepatic TEAE,
- at least one hepatic TEAE of Special Interest (AESI)
- at least one hyperpigmentation TEAE,
- at least one Adverse Events of Special Interest (AESI)
- at least one TEAE leading to death.

The frequency and incidence of TEAEs will be summarized by System Organ Class (SOC) and Preferred Term (PT) by Placebo, MT-7117 over all, MT-7117 [REDACTED] only, [REDACTED] to [REDACTED] regimen, [REDACTED] to [REDACTED] regimen. For this table, SOC is sorted by International order; then within SOC, PT is sorted by descending counts under MT-7117 Total group, then descending counts under Placebo group, then alphabetic order for PTs with the same count.

The AE summaries will be presented by treatment group for the following:

- TEAEs by SOC and PT
- TEAEs by SOC, PT and severity
- TEAEs by SOC, PT and relationship to study drug

- Treatment emergent adverse reactions by SOC and PT
- Treatment emergent adverse reactions by SOC, PT and severity
- Serious TEAEs by SOC and PT
- Serious TEAEs by SOC and PT and relationship to study drug
- Serious treatment emergent adverse reactions by SOC and PT
- TEAEs leading to drug withdrawn by SOC and PT
- Treatment emergent adverse reaction leading to drug withdrawn by SOC and PT
- Hepatic TEAEs by SOC and PT
- Hepatic TEAE of Special Interest (AESI) by SOC and PT
- Hyperpigmentation TEAEs by SOC and PT
- TEAEs of special interest by SOC and PT
- TEAEs by SOC and PT for TEAEs with frequency $\geq 5\%$ in total MT-7117 group

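### The dose-reduction columns in the SAP 8.3.1 AE tables understate any-TEAE incidence on the starting dose, because an intolerable AE decides who leaves the starting-dose-only column

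*SAP*

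**What the plan says.** **Grouping in the AE tables.** SAP 8.3.1 states: "The overall TEAEs are summarized by Placebo, MT-7117 over all, MT-7117 [REDACTED] only, [REDACTED] to [REDACTED] regimen", followed by a second reduction regimen. The TEAE table by system organ class and preferred term uses the same columns. The dose labels are redacted, but Protocol 8.1 gives the sequence: all active subjects start at 300 mg and may step down to 200 mg and then 100 mg.

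**Grouping in the safety population.** SAP 5.4 analyses subjects by treatment actually received and adds: "For subjects who took more than one treatment, the highest dose level will be used for safety analyses".

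**Default groups.** SAP 9.2 reports one pooled MT-7117 group against placebo unless otherwise specified. It lists separate dose groups only for CRISS and mRSS.

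**How a subject reaches a lower dose.** Protocol 8.1 and 10.1.3.1 tie a reduction to continuing intolerable AEs. For reductions initiated by the investigator, the criteria are "AEs which are classified as serious and/or moderate/severe (in severity), which did not improve with clinical management" and also "AEs assessed as having reasonable possibility of relationship to MT-7117 per Investigator's judgement". The move is one way: "Note: Dose up-titration after dose reduction is not allowed".

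**Counting.** Each event counts once per subject (SAP 8.3.1), and the denominator is the number of subjects in the group shown (SAP 6.1).

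**Caveat.** The end of SAP 8.2.1 concedes that randomization does not protect comparisons between dose-reduction regimens, but only for efficacy. SAP 8.3.1 has no such statement.

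**The concern.** A column headed with the full dose only invites the reader to take it as the tolerability of that dose. It is the tolerability among those who were never reduced. The event being tabulated is also the event that moves a subject out of the column, so AEs that began at 300 mg appear under a regimen named for a reduction.

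Protocol 8.2 makes the safety and tolerability of the selected 300 mg dose an aim. Protocol 8.2.2 reports that in an earlier Phase 2 study 300 mg had more TEAEs, severe TEAEs and discontinuations than 100 mg or placebo. A table that tends to show the opposite pattern because of how its columns are formed could mislead on that question. The SAP already recognises the problem for efficacy. It is more direct for safety, where an AE is the entry condition.

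**Working it through.** **Plan's own figure.** The documents give no figure for AEs by dose. The only calculated figure is the sample size (SAP 3.3), from which the 36 active subjects are taken. Noether's formula with a difference of 0.35 and SD 0.5 gives N = 72.7 and 79.6% power at 72, which agrees with the plan. Nothing below depends on that power.

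**Step 1: what each grouping does.** Every active subject starts at 300 mg and can only go down, so the highest dose taken is the starting dose for all of them. The 5.4 rule, used as a dose attribution, puts every active-arm AE on the starting dose, including AEs that begin after a reduction. The 8.3.1 columns split subjects by the path they followed. The two groupings err in opposite directions for the starting dose, and no visible table uses the dose at onset.

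**Step 2: algebra.** Let A of 36 active subjects have a TEAE on the starting dose, and let R of those A later reduce.

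- By dose at onset: A/36.
- Starting-dose-only column: (A−R)/(36−R).
- Reduction columns: R/R, about 100%.

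(A−R)/(36−R) < A/36 is equivalent to 36A − 36R < 36A − AR, that is, A < 36 whenever R > 0. The direction needs no assumed rate.

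**Step 3: size.** The documents give no AE or reduction rates, so A and R are assumptions.

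| A | A/36 | R = 4 | R = 9 | R = 14 |
|---|---|---|---|---|
| 22 | 61.1% | 18/32 = 56.25% | 13/27 = 48.1% | 8/22 = 36.4% |
| 27 | 75.0% | 23/32 = 71.9% | 18/27 = 66.7% | 13/22 = 59.1% |
| 32 | 88.9% | 28/32 = 87.5% | 23/27 = 85.2% | 18/22 = 81.8% |

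**Step 4: no true dose effect.** Simulate 36 active subjects for 12 months. Assume a 12% chance of an AE each month at every dose, with 30% of AEs leading to a step down.

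- Expected AEs in the arm: 36 × 12 × 0.12 = 51.8. The highest-dose rule credits all of them to the starting dose.
- AEs that began on the starting dose: 42.7 on average. AEs shown in the starting-dose-only column: 24.3.
- Any TEAE on the starting dose by onset: (15.5 + 12.8)/36, about 78%. In the starting-dose-only column: 15.5/23.2 = 66.6%. In the reduction columns: 100%.
- Rate by dose at onset: 1.44 per person-year on the starting dose and 1.45 on reduced doses.

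**Step 5: the exception.** Subjects who withdraw straight from the starting dose stay in its column while reducers leave the denominator. Two such subjects are 2/36 = 5.6% of the arm, but 2/27 = 7.4% of the column when R = 9.

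**Step 6: is dose at onset unbiased?** The equal rates in step 4 arise because the simulated subjects are identical. Now let the intolerable-AE hazard be 0.4 per year at every dose, multiplied by a gamma frailty with mean 1 and variance 1 (an assumption). Each subject steps down at each event, and follow-up at the lowest dose is counted to the first event there. Over one year:

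- Starting dose: events 1 − 1/1.4 = 0.2857; person-years ln(1.4)/0.4 = 0.8412; rate 0.34.
- One step down: events 0.2857² = 0.0816; person-years 2.5 × (ln 1.4 + 1/1.4 − 1) = 0.1269; rate 0.64.
- Two steps down: events 0.2857³ = 0.0233; person-years 2.5 × [ln 1.4 − 2(1 − 1/1.4) + 0.5(1 − 1/1.96)] = 0.0249; rate 0.94.

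The rates rise as the dose falls although dose has no effect, because only intolerant subjects contribute time at the lower doses.

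**The case against.** The strongest reply is that the comparison that answers the safety objective, MT-7117 overall versus placebo, stands in the same tables and is untouched. The tables are descriptive, every AE is listed, and no objective calls for a dose comparison. All of this stands, and it limits the weight of the point.

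Three stronger readings are tempting and should not be made.

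- **That SAP 5.4 empties the reduced columns or causes the undercount.** The 8.3.1 columns are dosing paths, not dose levels. A subject on a path that starts at 300 mg still has 300 mg as highest dose, so 5.4 does not empty the column. Taken literally, 5.4 overcredits the starting dose. It can also be read as a rule for deciding active or placebo. What remains is that the SAP does not say how the two groupings relate.
- **That the tables show an inverse dose–AE pattern whatever the truth.** Protocol 9.5 allows withdrawal without a prior reduction, including on liver criteria. Protocol 8.1 calls for conservative management at the starting dose first, and 10.1.3.2 says only that reduction should be considered. Intolerable AEs can therefore remain in the starting-dose-only column, and those leading to withdrawal can be more frequent there.
- **That tables by dose at onset would give the true dose relation and should replace the regimen tables.** Step 6 of the working shows that they carry a selection effect of their own.

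The redacted labels, and the table shells and iDMC analysis plan not being among the documents, mean only that no onset-dose table is visible, not that none exists.

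**Conclusion.** The point holds in a limited form. In the 8.3.1 regimen columns, the incidence of any TEAE and of reduction-triggering AEs on the starting dose is understated by construction, and the reduction columns sit close to 100% for any TEAE. The direction follows from the plan's own rules, provided that some subjects reduce (R > 0) and not every active subject has a TEAE on the starting dose (A < 36).

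The size depends on rates the documents do not give. Over the assumed grid the shortfall runs from 1.4 percentage points (88.9% to 87.5%) to 24.7 (61.1% to 36.4%), with 8.3 points in the central case (75.0% to 66.7%). AEs leading directly to withdrawal can go the other way. The randomized safety comparison is not affected, so this is a cheap improvement to a descriptive table.

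**What to change.** 1. Keep MT-7117 overall versus placebo as the safety comparison.
2. In SAP 5.4, limit the highest-dose sentence to assigning subjects to active or placebo. In 8.3.1, state which tables use the regimen columns and which use the default groups of 9.2.
3. Add, without removing the regimen tables, summaries of TEAEs, serious TEAEs, adverse reactions, and hepatic and hyperpigmentation TEAEs by dose at AE onset (each dose level and off drug), with events and person-time.
4. Carry the 8.2.1 caveat into 8.3.1 and footnote the regimen tables: membership is defined by having had an AE.

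The data exist. Protocol 10.1.3.1 says "The date of dose reduction visit and the reason will be recorded in the eCRF", and AE start dates are collected. The SAP should also say which dose applies to an AE starting on the day of a reduction. It should flag AEs with imputed start dates, because the early-date imputation in SAP 7.1.3.1 can move an event to the higher dose.

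The cost is SAP wording and some programming. The SAP should state two limits: person-time at the reduced doses will be short and its rates imprecise, and it comes only from subjects already selected for intolerance, so the onset-dose rates are descriptive and not an unbiased dose comparison.
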